5.7 Primary and secondary outcomes at 45 days of Follow-up

A Table of the primary and secondary outcomes at 45-day visit will be produced, randomized to Amulet vs randomized to Watchman

Table 4. Primary and secondary outcomes at 45 days

	Watchman/FLX	Amulet	Amulet vs Watchman Mean difference (95% CI)	p-value
	N = xx	N = xx		
Patent Appendage or justified cross-over to non-randomized device	n = xx, xx (%)	n = xx, xx (%)	x.x% (x.x%; x.x%)	x.XXX
Patent Appendage*	n = xx, xx (%)	n = xx, xx (%)	x.x% (x.x%; x.x%)	x.XXX
Justified cross-over to non-randomized device¶	n = xx, xx (%)	n = xx, xx (%)	x.x% (x.x%; x.x%)	x.XXX
Death	n = xx, xx (%)	n = xx, xx (%)	x.x% (x.x%; x.x%)	x.XXX
Cardiovascular death	n = xx, xx (%)	n = xx, xx (%)	x.x% (x.x%; x.x%)	x.XXX
Cerebrovascular event	n = xx, xx (%)	n = xx, xx (%)	x.x% (x.x%; x.x%)	x.XXX
Stroke	n = xx, xx (%)	n = xx, xx (%)	x.x% (x.x%; x.x%)	x.XXX
ischaemic stroke	n = xx, xx (%)	n = xx, xx (%)	x.x% (x.x%; x.x%)	x.XXX
haemorrhagic stroke	n = xx, xx (%)	n = xx, xx (%)	x.x% (x.x%; x.x%)	x.XXX
TIA	n = xx, xx (%)	n = xx, xx (%)	x.x% (x.x%; x.x%)	x.XXX
Systemic or pulmonary embolism	n = xx, xx (%)	n = xx, xx (%)	x.x% (x.x%; x.x%)	x.XXX
Systemic embolism	n = xx, xx (%)	n = xx, xx (%)	x.x% (x.x%; x.x%)	x.XXX
Pulmonary embolism	n = xx, xx (%)	n = xx, xx (%)	x.x% (x.x%; x.x%)	x.XXX
Myocardial infarction	n = xx, xx (%)	n = xx, xx (%)	x.x% (x.x%; x.x%)	x.XXX
Device embolization	n = xx, xx (%)	n = xx, xx (%)	x.x% (x.x%; x.x%)	x.XXX
Bleeding	n = xx, xx (%)	n = xx, xx (%)	x.x% (x.x%; x.x%)	x.XXX
BARC 2	n = xx, xx (%)	n = xx, xx (%)	x.x% (x.x%; x.x%)	x.XXX
BARC 3abc	n = xx, xx (%)	n = xx, xx (%)	x.x% (x.x%; x.x%)	x.XXX
BARC 4	n = xx, xx (%)	n = xx, xx (%)	x.x% (x.x%; x.x%)	x.XXX
BARC 5ab	n = xx, xx (%)	n = xx, xx (%)	x.x% (x.x%; x.x%)	x.XXX
BARC 3-5	n = xx, xx (%)	n = xx, xx (%)	x.x% (x.x%; x.x%)	x.XXX
TIMI major or minor	n = xx, xx (%)	n = xx, xx (%)	x.x% (x.x%; x.x%)	x.XXX
TIMI major	n = xx, xx (%)	n = xx, xx (%)	x.x% (x.x%; x.x%)	x.XXX
TIMI minor	n = xx, xx (%)	n = xx, xx (%)	x.x% (x.x%; x.x%)	x.XXX
TIMI minimal	n = xx, xx (%)	n = xx, xx (%)	x.x% (x.x%; x.x%)	x.XXX
GUSTO moderate or severe	n = xx, xx (%)	n = xx, xx (%)	x.x% (x.x%; x.x%)	x.XXX
GUSTO severe	n = xx, xx (%)	n = xx, xx (%)	x.x% (x.x%; x.x%)	x.XXX
GUSTO moderate	n = xx, xx (%)	n = xx, xx (%)	x.x% (x.x%; x.x%)	x.XXX
GUSTO mild	n = xx, xx (%)	n = xx, xx (%)	x.x% (x.x%; x.x%)	x.XXX
Patient on (N)OAC at 45 days visit	n = xx, xx (%)	n = xx, xx (%)	x.x% (x.x%; x.x%)	x.XXX

Data expressed as n (%), p-value from Fisher's tests

¶ Justified crossover is defined as the switch from the randomized device to the other device based on morphological/anatomical considerations during device implantation as centrally assessed by an independent and multidisciplinary clinical event committee (CEC). This parameter was included in the composite primary outcome together with *LAA Patency.

CCTA: cardiac computer tomography angiography. TTE: Transthoracic Echocardiography.

CTU Bern	Swiss APERO SAP	Version: 2.0	
	Template: CS_STA_TEM-11	Valid from: 17.08.2021	

5.8 LAA assessments at 45 days of Follow-up

A Table of the LAA assessments (CCTA by the Core laboratory, TEE by the local teams) at 45-day visit will be produced, randomized to Amulet vs randomized to Watchman.

Table 5. Imaging assessment at 45 days visit

	Watchman/FLX N = xx	Amulet N = xx	Amulet vs Watchman Mean difference (95% p-value
CCTA assessment			
45day CCTA performed	n = xx, xx (%)	n = xx, xx (%)	x.x% (x.x%; x.x%)
Linear attenuation HU— mean (SD) ¶	n = xx, mean + sd	n = xx, mean + sd	x.XXX
Patent LAA — no. (%) ¶	n = xx, xx (%)	n = xx, xx (%)	x.XXX
LAA HU \geq 100 arterial phase — no. (%) ¶	n = xx, xx (%)	n = xx, xx (%)	x.XXX
LAA HU \geq 25% arterial phase — no. (%) ¶	n = xx, xx (%)	n = xx, xx (%)	x.XXX
Peridevice leak (PDL) — no. (%) ¶	n = xx, xx (%)	n = xx, xx (%)	x.XXX
Mixed leak (ML) — no. (%) ¶	n = xx, xx (%)	n = xx, xx (%)	x.XXX
Intradevice leak (IDL) — no. (%) ¶	n = xx, xx (%)	n = xx, xx (%)	x.XXX
Patent LAA with no visible leak — no. (%) ¶	n = xx, xx (%)	n = xx, xx (%)	x.XXX
Linear attenuation HU — mean venous phase (SD) ¥	n = xx, mean + sd	n = xx, mean + sd	n = xx, mean + sd
LAA patency venous phase — no. (%) ¥	n = xx, xx (%)	n = xx, xx (%)	x.XXX
LAA HU \geq 100 venous phase — no. (%) ¥	n = xx, xx (%)	n = xx, xx (%)	x.XXX
LAA HU on venous phase \geq 150% of LAA HU on arterial phase images — no. (%) ¥	n = xx, xx (%)	n = xx, xx (%)	x.XXX
Potential thrombus — no. (%)	n = xx, xx (%)	n = xx, xx (%)	x.XXX
Device related thrombus — no. (%)	n = xx, xx (%)	n = xx, xx (%)	x.XXX
TEE assessment			
45day TEE performed	n = xx, xx (%)	n = xx, xx (%)	x.XXX
Peridevice leak PDL — no. (%)	n = xx, xx (%)	n = xx, xx (%)	x.XXX
first PDL — no. (%)	n = xx, xx (%)	n = xx, xx (%)	x.XXX
PDL leak width — mm mean(SD)	n = xx, mean + sd	n = xx, mean + sd	n = xx, mean + sd
second PDL — no. (%)	n = xx, xx (%)	n = xx, xx (%)	x.XXX
PDL leak width — mm mean(SD)	n = xx, mean + sd	n = xx, mean + sd	n = xx, mean + sd
Any PDL width \geq 3mm — no. (%)	n = xx, xx (%)	n = xx, xx (%)	x.XXX
Device related thrombus — no. (%)	n = xx, xx (%)	n = xx, xx (%)	x.XXX

Data expressed as n (%), p-value from Fisher's tests) or means \pm standard deviations (p-value from unpaired t-tests) or median[IQR] (p-value from Mann-Whitney U-test).

CCTA: cardiac computer tomography angiography assessed by Core Laboratory. TEE: Transoesophagus Echocardiography assessed by local team.

Mixed PDL: PDL transferring into intradevice leak, or intradevice leak transferring into

[figure not shown]
¶: In x of xx CCTAs performed, LAA patency was not assessable (n=xx)

¥: in x of xx CCTAs the venous phase scan was not performed (n=xx)

CTU Bern	Swiss APERO SAP	Version: 2.0	
	Template: CS_STA_TEM-11	Valid from: 17.08.2021	

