Measurements and procedures:	
Patients with indication to LAA closure will be randomly assigned in a 1:1 ratio to Amulet or Watchman/FLX device implantation. In the event that the patient is randomized to the Watchman/FLX arm, the operator will be able to choose, on the basis of clinical reasons, if implant Watchman or the new generation Watchman FLX (if available in the center). Study procedures will be as follows:
 
 • A CCTA will be performed before the procedure as per standard of care in order to obtain the morphological features of LAA (useful for the procedure planning) and to exclude the presence of LAA thrombus. • Implantation will be performed according to device specific instruction for use and latest consensus document⁵, based on preprocedural CCTA images, TEE guidance and angiography. • After the procedure, patients will receive acetylsalicylic acid (ASA) and clopidogrel or (N)OAC at discretion of the treating physician (according to the bleeding risk, the stroke risk and intra-procedural TEE evaluation) for 45 days and then will undergo TEE as well as CCTA assessment. 
 ◦ If a residual peridevice leak flow > 5 mm or a residual intra-cardiac thrombus is detected, treatment with ASA and (N)OAC should be considered up a sequential TEE evaluation at 6 months. Final decision to implement an OAC regimen with or without ASA will eventually be left to the discretion of the treating physician taking the ischemic and bleeding risk into account; ◦ If residual peridevice leak flow ≤ 5 mm, patients will receive ASA and clopidogrel or (N)OAC (at discretion of the treating physician according to the bleeding and stroke risks) up until 3 months after procedure. Thereafter, monotherapy with ASA will be continued until 12 months after procedure. 
Further follow-ups will take place at 13 months and yearly until 5 years.

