17.13 LAA PATENCY ASSESSED BY TEE

At 45 days after LAAC, patients will undergo a TEE assessment (and a CCTA as well). Device deployment will be assessed from 0° to 135° (0° - 45° - 90° - 135°) with and without color Doppler (using a scale 50-60 cm/sec). Presence of leak will be locally ascertained by expert echocardiographers with extensive previous and ongoing work imaging on LAAC devices. Leak on TEE is defined as any jet between LAA and LA or conversely detectable by means of color-Doppler (high velocity 50-60 cm/sec). The size is measured taking the narrowest flow region of the jet that occurs at, or just close to, the device.

Of note, rate of LAA patency at 45 day CCTA will be compared with rate of leak at 45 day TEE.

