6.1.2 Secondary outcome

Secondary outcomes are:

- *LAA patency (arterial and/or venous phase) at 45 day CCTA and 13-month CCTA in the per protocol and as treated populations*
- *All cause of death, stroke, systemic or pulmonary embolism and spontaneous MI*
- *Cardiovascular death*
- *Ischemic stroke*
- *Hemorrhagic stroke*
- *Bleeding events according to the BARC classification at each follow-up.*
- *Procedure-related complications*
- *Rate of patients on (N)OAC at 45 days and 6 months*
- *Device related thrombosis at 45 day TEE/CCTA and 13-month CCTA in the per protocol and as treated populations*
- *Feasibility outcome (number of device implantation attempts, total time procedure, x-ray dose and total contrast dose used in the procedure)*
- *LAA patency at 45 day TEE in the per protocol and as treated populations*

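### SAP Table 5 compares TEE leak width between arms only among patients who have a leak, so its difference and p-value are not a randomised comparison and can point the wrong way

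*Combined protocol and SAP*

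**What the plan says.** SAP section 5.8 announces a table of imaging assessments "at 45-day visit will be produced, randomized to Amulet vs randomized to Watchman". The comparison column is headed as an Amulet versus Watchman mean difference. In the TEE block the order is: any peridevice leak (count and percentage), first leak (count), "PDL leak width — mm mean(SD"), second leak (count), the same width row again, then any leak of 3 mm or more (count). Each width row has its own n.

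The table footnote assigns tests by type of summary; for means it gives "p-value from unpaired t-tests". SAP 4.1 says that continuous variables will be compared by a two-sided unpaired t test or a Mann-Whitney test.

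Protocol Appendix 1, section 17.13 fixes what a width is. "Leak on TEE is defined as any jet between LAA and LA or conversely detectable by means of color-Doppler", and "The size is measured taking the narrowest flow region of the jet that occurs at, or just close to, the device". Neither document assigns a width to a patient without a jet.

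Mean width is not a listed outcome. The listed TEE outcome in SAP 6.1.2 is "LAA patency at 45 day TEE in the per protocol and as treated populations", and protocol 5.1 and SAP 1.2 give the TEE patency criterion as residual flow of 3 mm or more.

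**The concern.** A patient enters a width row only by having a leak. That is an outcome observed after randomisation, and it is what the trial expects the devices to change: the primary objective is superiority in appendage occlusion. Patients with a leak in one arm need not be comparable with patients with a leak in the other, so a difference and p-value between them do not have the protection of randomisation, whatever their sign.

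At stake is a false reading of the TEE data. If one device closes small leaks and leaves larger ones as they were, its remaining leaks are larger on average. The table would then suggest fewer but wider leaks, although no patient has a wider leak than with the other device. The split into first and second leak also means that no row gives each patient's largest leak.

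**Working it through.** **What the plan states.** The documents give no power, leak-width distribution or expected difference for TEE width, so there is no plan figure to reproduce on this point. The arm size comes from the primary sample size (SAP 2.3: 200 patients, 50% versus 30%, 5% level, more than 80% power). Two-sided, pooled variance under the null: (0.20 − 1.96 × √(2 × 0.40 × 0.60/100)) / √(0.25/100 + 0.21/100) = (0.20 − 0.1358)/0.0678 = 0.947, power 82.8%. It reproduces with 100 per arm.

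**Inputs for the illustration.**
- Leak rates, scenario 1: 37% versus 14.9%, from the retrospective series in protocol 3.1. It concerns the predecessor ACP device and is used only for scale.
- Leak rates, scenario 2: 36%, the TEE rate in another series in protocol 3.1, versus 24%, which is assumed.
- Widths: gamma with mean 3 mm and SD 1.0, 1.5 or 2.0 mm, all assumed.
- 100 patients per arm, 3,000 simulated trials per setting, t-test among patients with a leak.

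**Mechanism A: smallest leaks sealed, larger ones unchanged** (Watchman/FLX versus Amulet).

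| Leak rates | SD (mm) | Mean among leakers (mm) | Trials significant for Amulet wider | Mean over all patients, no leak = 0 (mm) | Share with 3 mm or more |
|---|---|---|---|---|---|
| 37% to 14.9% | 1.0 | 3.00 vs 3.97 | 92% | 1.11 vs 0.59 | 16.9% vs 14.9% |
| 37% to 14.9% | 1.5 | 3.00 vs 4.45 | 90% | 1.11 vs 0.66 | 16.1% vs 14.8% |
| 37% to 14.9% | 2.0 | 3.01 vs 4.91 | 87% | 1.12 vs 0.73 | 15.3% vs 14.8% |
| 36% to 24% | 1.0 | 3.00 vs 3.51 | 54% | 1.08 vs 0.85 | 16.4% vs 16.5% |
| 36% to 24% | 1.5 | 3.01 vs 3.74 | 49% | 1.08 vs 0.90 | 15.6% vs 15.7% |
| 36% to 24% | 2.0 | 3.01 vs 3.93 | 43% | 1.08 vs 0.94 | 14.8% vs 14.8% |

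The leakers-only mean moves against the device that seals better. The all-patient mean keeps the right direction.

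**Mechanism B: leaks sealed regardless of size.** The means among leakers are equal (3.0 versus 3.0 mm), and Amulet is significantly wider in about 3% of trials. No distortion.

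**Mechanism C: every leak narrowed by a constant, so that small ones close.** The mean among leakers falls to between 0.84 and 2.06 mm. Amulet is significantly wider in 0% of trials and significantly narrower in 46% to 100%.

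**Second width model, which can be checked by hand.** Assume 95 TEEs per arm, 35% leaking with Watchman/FLX, exponential widths with mean 2.5 mm, and the smallest 40% sealed.
- Cut-off: −2.5 × ln(0.6) = 1.28 mm.
- Mean among the remaining leakers: 2.5 + 1.28 = 3.78 mm, against 2.50 mm. The difference is +1.28 mm.
- All-patient means: 0.35 × 2.5 = 0.875 mm versus 0.21 × 3.78 = 0.79 mm. The difference is −0.08 mm.
- Share with 3 mm or more: 0.35 × exp(−3/2.5) = 10.5% in both arms.
- In 5,000 simulated trials the t-test is significant for Amulet wider in 44%.

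Under the same model, sealing 40% of leaks at random, or narrowing all leaks by 1.28 mm, gives a leakers-only difference of about 0 mm, with Amulet significantly wider in about 3% of trials. In the narrowing case the all-patient mean does fall, by 0.35 × 2.5 − 0.21 × 2.5 = 0.35 mm. The leakers-only row would then miss a real benefit.

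**The case against.** **The restriction to leakers is inferred.** The SAP never says it in words. This stands as a caution, but width needs a jet, the rows sit under leak counts with their own n, and no 0 mm rule exists. No other reading is workable.

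**The test on these rows is not certain.** In the readable text of Table 5 the comparison cell of both width rows holds a mean-and-SD placeholder, the header is damaged, and the footnote covers all rows and also names Fisher and Mann-Whitney tests. This stands in part. Table 5 alone does not prove a t-test on width, but the arm-by-arm layout, the column heading and the general rule in SAP 4.1 point to a between-arm test of some kind. A Mann-Whitney test among leakers would have the same selection.

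**The table already protects the reader.** This largely stands. In the exponential example a reader would see any leak in 35% versus 21% and leaks of 3 mm or more in 10.5% of both arms: fewer leaks, and no more large ones. The 3 mm row alone does not show why the means differ, so the reader has to combine rows, and Table 5 carries no caution. SAP 5.9 does carry one for the device-specific tables.

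**Stronger readings.** A reader might infer that a better-sealing device will look worse in this row. The documents do not support that: they give no TEE widths and no sealing mechanism, and mechanisms B and C give no distortion or the opposite sign. A reader might also treat the missing row above 5 mm as an omitted endpoint. The protocol uses that size as a condition ("If a residual peridevice leak flow > 5 mm or a residual intra-cardiac thrombus is detected") for considering treatment, with the final decision left to the physician; the stated TEE patency criterion is 3 mm. The 5 mm cut-off is useful for description, and its absence is not an error.

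**Conclusion.** The point holds as a minor one. Table 5, read with SAP 4.1, compares TEE leak width between randomised arms within a subset selected on a post-randomisation outcome. Any difference or p-value there is not a randomised comparison. Under one plausible mechanism it has the wrong sign: +0.5 to +1.9 mm among leakers, significant in 43% to 92% of simulated trials over the settings shown. Under the other mechanisms it is neutral or points the other way.

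These sizes rest on assumed widths, an assumed 24% leak rate in scenario 2 and leak rates borrowed from small or predecessor-device series. They show what can happen and do not forecast this trial.

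The effect is confined to two supportive rows. The any-leak and 3 mm rows remain valid if their denominator is all patients with a 45-day TEE, and the primary CCTA composite is not affected.

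**What to change.** In SAP Table 5:

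1. Label both width rows as among patients with a leak, descriptive only, and leave the difference and p-value cells empty.
2. If leak size is to be compared between arms, derive each patient's largest leak over all patients with a 45-day TEE, with 0 mm where no leak is seen. Show it as ordered categories (none, below 3 mm, 3 to 5 mm, above 5 mm), using cut-offs already in the protocol, with a rank-based test.
3. State the denominator of the any-leak and 3 mm rows.

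The cost is SAP wording, one derived variable and a few table rows; no new data. The gain in sensitivity is modest. Most values tie at 0 mm (65% and 79% in the exponential example), so the rank test largely tracks whether a leak is present. In that example a Mann-Whitney test on the all-patient widths is significant in 39% of trials, against about 52% for Fisher's test on any leak. The reason for the change is a valid comparison of size, not more power.

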5.9 Evaluation of Amulet and Watchman implantations

A Table of the Amulet implantation assessment post-procedure and at 45 days will be produced (according to actual device implanted). Similarly, a separate Table with the Watchman implantation assessment post-procedure and at 45 days will be produced (according to actual device implanted). Note that these assessments are not directly comparable across the devices, as these assessments depend on the shape and the structure of the device, e.g. Amulet has lobes with a separate disk, whereas the Watchman only has lobes.

CTU Bern	Swiss APERO SAP	Version: 2.0
	Template: CS_STA_TEM-11	Valid from: 17.08.2021

Supplemental Table 1. Evaluation of Amulet / ACP implantation post-procedure and at 45 days visit

Amulet ACP implanted (N=xx)	
Post-procedural TEE assessment	
Is the disc over the left lateral ridge LLR? — no. (%)	x (x.x%)
Distance disc from LLR — mm (SD)	n = xx, xx.x ± x.x
Complete occlusion of the ostium by the disc	x (x.x%)
Concavity of the disc — no. (%)	n = xx, xx.x ± x.x
Separation lobe from the disc >2mm — no. (%)	x (x.x%)
Lobe's shape	
tire — no. (%)	x (x.x%)
strawberry/bell — no. (%)	x (x.x%)
square — no. (%)	x (x.x%)
Angle between lobe-axis and disc-axis of the device — degrees angulation (SD)	n = xx, xx° ± x°
Minimum device diameter — mm (SD)	n = xx, xx.x ± x.x
Partial prolapse of the lobe into left appendage* — no. (%)	x (x.x%)
Peridisk leak PDiL¶ — no. (%)	x (x.x%)
one PDiL — no. (%)	x (x.x%)
two PDiL — no. (%)	x (x.x%)
45 days visit CCTA assessment	
Is the disc over the left lateral ridge LLR? — no. (%)	x (x.x%)
Distance disc from LLR — mm (SD)	n = xx, xx.x ± x.x
Concavity of the disc — mm (SD)	n = xx, xx.x ± x.x
Lobe's shape	
tire — no. (%)	x (x.x%)
strawberry/bell — no. (%)	x (x.x%)
square — no. (%)	x (x.x%)
Separation lobe-disc maximum — mm (SD)	n = xx, xx.x ± x.x
Separation lobe-disc minimum — mm (SD)	n = xx, xx.x ± x.x
Angle between lobe-axis and disc-axis of the device — degrees angulation (SD)	n = xx, xx° ± x°
Lobe diameter minimum — mm (SD)	n = xx, xx.x ± x.x
Lobe diameter maximum — mm (SD)	n = xx, xx.x ± x.x
Partial prolapse of the lobe into left appendage* — no. (%)	x (x.x%)
Peridisk leak PDiL¶ — no. (%)	x (x.x%)
one PDiL — no. (%)	x (x.x%)
two PDiL — no. (%)	x (x.x%)

Only successfully implanted LAAC devices evaluated.

*width of the lobe is $<2/3$ within the circumflex artery.

CTU Bern	Swiss APERO SAP	Version: 2.0	
	Template: CS_STA_TEM-11	Valid from: 17.08.2021	

¶leak visible between the disc and the lobe, but only measured if distance between disc and lobe large enough to allow assessment of hue.

CCTA: cardiac computer tomography angiography assessed by Core Laboratory. TEE: Transthoracic Echocardiography assessed by local team.

includes n=x patient randomized to Watchman / FLX, but were implanted a cross-over Amulet device instead.

Supplemental Table 2. Evaluation of Watchman / FLX implantation post-procedure and at 45 days visit

Watchman / FLX implanted (N=xx)
--

Post-procedural TEE assessment

Maximum device diameter TEE — mm (SD)	n = xx, xx.x ± x.x
Maximum device compression* — % (SD)	n = xx, xx.x ± x.x
Minimum device diameter TEE — mm (SD)	n = xx, xx.x ± x.x
Minimum device compression¶ — % (SD)	n = xx, xx.x ± x.x
Lobe's shape	
inverted — no. (%)	x (x.x%)
marshmallow — no. (%)	x (x.x%)
bell — no. (%)	x (x.x%)
hotdog — no. (%)	x (x.x%)
Position of device from LAA ostium	
at the same level — no. (%)	x (x.x%)
distally — no. (%)	x (x.x%)
proximally — no. (%)	x (x.x%)
Position of the device in respect to the left lateral ridge LLR?	
at the same level — no. (%)	x (x.x%)
distally — no. (%)	x (x.x%)
proximally — no. (%)	x (x.x%)
How far is the Watchman device off-axis to the LAA axis — degrees angulation (SD)	n = xx, xx° ± x°

45 days visit CCTA assessment

Minimum device diameter — mm (SD)	n = xx, xx.x ± x.x
Minimum device compression¶ — % (SD)	n = xx, xx.x ± x.x
Maximum device diameter — mm (SD)	n = xx, xx.x ± x.x
Maximum device compression* — % (SD)	n = xx, xx.x ± x.x
Lobe's shape	
inverted — no. (%)	x (x.x%)
marshmallow — no. (%)	x (x.x%)
bell — no. (%)	x (x.x%)
hotdog — no. (%)	x (x.x%)
Position of device from LAA ostium	
at the same level — no. (%)	x (x.x%)

CTU Bern	Swiss APERO SAP	Version: 2.0	
	Template: CS_STA_TEM-11	Valid from: 17.08.2021	

distally — no. (%)	x (x.x%)
proximally — no. (%)	x (x.x%)
Position of the device in respect to the left lateral ridge LLR?	
at the same level — no. (%)	x (x.x%)
distally — no. (%)	x (x.x%)
proximally — no. (%)	x (x.x%)
How far is the device from the left lateral ridge LLR? — mm (SD)	n = xx, xx.x ± x.x
How far is the Watchman device off-axis to the LAA axis — degrees angulation (SD)	n = xx, xx° ± x°

Only successfully implanted LAAC devices evaluated.

*(Manufacturer device diameter - maximum implanted device diameter)*100%

¶(Manufacturer device diameter - minimum implanted device diameter)*100%

CCTA: cardiac computer tomography angiography assessed by Core Laboratory. TEE: Transthoracic Echocardiography assessed by local team.

includes n=x patient randomized to Amulet / ACP, but were implanted a cross-over Watchman device instead.

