8. STUDY INTERVENTION

8.1 Identity of Investigational Medicinal Devices

The WATCHMAN (Atritech, Boston Scientific, Natick, MA, USA) LAAC technology consists of the Access System (Access Sheath and Dilator) and Delivery System (Delivery Catheter and WATCHMAN Device). The Access System and Delivery System permit Device placement in the left atrial appendage (LAA) via femoral venous access and inter-atrial septum crossing into the left atrium. WATCHMAN device is a self-expanding nitinol structure with a porous covering on the proximal face. The device is constrained within the Delivery System until deployment in the LAA. The Device is available in 5 sizes from 21 to 33 mm. The new generation Watchman FLX has a shorter device length and a less taper angle to simplify implantation and to fit a wider range of patients. Furthermore, the frame of the new device is designed to enhance sealing within the left atrial appendage.

The AMPLATZER Amulet (St. Jude Medical-Abbott) is a self-expanding device made of nitinol that has a distal lobe and a proximal disc, connected by an articulated waist. The device lobe has six to 10 pairs of stabilising wires and is meant to be implanted in the proximal 10-15 mm of the left atrial appendage (LAA), whereas the device disc is intended to cover the ostium at the left atrial side. The proximal female screw is recessed to minimise thrombus formation on the disc and potentially facilitate re-attachment of the device to the pusher screw. The lobe sizes range from 16 to 34 mm.

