10.2.2 Adjunctive CCTA criteria for LAA closure

In order to evaluate the complete LAA occlusion with the CCTA, we proposed following criteria

Amulet-CT criteria for LAA occlusion	Watchman/FLX -CT criteria for LAA occlusion
Lobe compression >10%	Position: plane of maximum diameter of the device is at or just distal (<2 mm) to the orifice of the LAA, and that it spans the entire LAA ostium. Position of the lobe in relation to left lateral ridge
Disc-lobe separation (>2 mm)	Size: measure the plane of the maximum diameter of the device, ensuring the threaded insert is visible. The device should be 80-92% of the original size
Device axis consistent with landing zone and landing zone and angle between disc and lobe	Seal: no contrast in the distal lobes
Concave disc	Consistency between device axis and ostium
Width of the lobe is $\geq 2/3$ within the circumflex artery and position of the disc in relation to left lateral ridge	Lobe's shape
Lobe's shape	

Lobe compression (%) was calculated as: $[(\text{manufacturer device diameter} - \text{measured diameter})/\text{manufacturer device diameter}] \times 100\%$

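### The two compression footnotes in SAP Supplemental Table 2 leave out the division by manufacturer device diameter, and the row labels they serve are misleading

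*Combined protocol and SAP*

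**What the plan says.** SAP section 5.9 plans a separate descriptive table for patients who actually received a Watchman/FLX (Supplemental Table 2). It has a post-procedural TEE block and a 45-day CCTA block, and each block has two compression rows: "Maximum device compression* — % (SD") and "Minimum device compression¶ — % (SD"). Diameters in the same table are in millimetres, for example "Maximum device diameter TEE — mm (SD").

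The footnotes define the two compression quantities:

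- Maximum row: "Manufacturer device diameter - maximum implanted device diameter)*100" per cent.
- Minimum row: "Manufacturer device diameter - minimum implanted device diameter)*100" per cent.

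Protocol 10.2.2 also defines compression. Beneath its table of CT criteria for both devices, the note opening "Lobe compression (%) was calculated as" takes manufacturer diameter minus measured diameter, divides by manufacturer diameter, and multiplies by 100%. The Watchman/FLX size criterion in that table is also relative to nominal size: "The device should be 80-92% of the original size". It is assessed in the plane of the device's maximum diameter.

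**The concern.** A percentage compression has to be a ratio. The SAP footnotes give a length multiplied by 100, which is not a percentage and which grows with device size at the same relative compression. A programmer who followed the SAP to the letter would fill four rows with values far from those of the protocol formula.

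The labels are a second, smaller problem. Compression falls as the measured diameter rises, so the row called maximum compression holds the lesser of the two values. A reader who sees only the row names would take them the wrong way round.

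What is at stake is the readability of these rows. Protocol 9.2 and SAP 2.7 say the adjunctive CCTA criteria are collected so that they can be validated, and size relative to nominal is one of those criteria for Watchman/FLX. The plausibility checks in SAP 3.2 and the double programming in SAP 6.7 name only primary and secondary outcomes, so neither formally covers this table.

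**Working it through.** The plan states no compression value of its own, so there is no figure to reproduce. The check puts the same inputs through both formulas.

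**Inputs**

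- Manufacturer diameter D: protocol 8.1 states "The Device is available in 5 sizes from 21 to 33 mm" for the Watchman. It gives no size range for the FLX, so 21 to 33 mm is used for both. D = 27 mm is taken as a mid-range value.
- Measured diameter d: 92% and 80% of D, the ends of the protocol 10.2.2 size range.

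**Formulas**

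- SAP footnotes: (D − d) × 100%
- Protocol 10.2.2: (D − d)/D × 100%

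**Results**

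| D (mm) | d (mm) | D − d (mm) | SAP as written | Protocol |
|---|---|---|---|---|
| 21 | 19.32 (92%) | 1.68 | 168% | 8% |
| 21 | 16.80 (80%) | 4.20 | 420% | 20% |
| 27 | 24.84 (92%) | 2.16 | 216% | 8% |
| 27 | 21.60 (80%) | 5.40 | 540% | 20% |
| 33 | 30.36 (92%) | 2.64 | 264% | 8% |
| 33 | 26.40 (80%) | 6.60 | 660% | 20% |

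The SAP value is the protocol value multiplied by D in millimetres, so the inflation is not a constant factor. A 10% compression would print as 210% for a 21 mm device and 330% for a 33 mm device. A printed mean over mixed sizes could not be converted back without the individual device sizes.

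**Labels**

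Since d_max ≥ d_min, D − d_max ≤ D − d_min. Take a 27 mm device with assumed measurements of 24 mm maximum and 22 mm minimum:

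- Row labelled maximum: (27 − 24) × 100 = 300% as written; 3/27 = 11.1% with the divisor.
- Row labelled minimum: (27 − 22) × 100 = 500% as written; 5/27 = 18.5% with the divisor.

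The order is the same under both formulas, so adding the divisor does not make the labels clear.

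**The case against.** **The slip would be caught.** The rows are declared in per cent, their placeholders have two digits before the decimal point, and the protocol prints the full formula. The first output would look absurd. This is probably true of the divisor, although the placeholders are generic. It is a reason to rate the point low, not to leave a wrong definition in the SAP.

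**The divisor was lost when the PDF was read.** This cannot be wholly excluded. However, both footnotes are complete one-line expressions with closed brackets, both lack the divisor, and the protocol's divisor came through.

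**The protocol formula is for the Amulet.** It is worded for lobe compression, and that term appears as a criterion only in the Amulet column. The protocol does not expressly extend it to Watchman/FLX. But the note sits beneath a table for both devices, and the Watchman/FLX criterion is itself a ratio to original size, so the same divisor is the reasonable reading.

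**The labels are not an error.** A reader might infer that the maximum and minimum labels are simply reversed and that values will land in the wrong rows. The documents do not support that. In both the TEE and CCTA blocks, each compression row directly follows the diameter row of the same name, and the footnote fixes which diameter goes in. The likely meaning is compression at that diameter. This objection stands: the labels mislead, but they cause no computational error.

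**The size criterion can still be checked.** A reader might also infer that the trial could not relate its data to the 80-92% range. That goes too far. Measured diameters are in the same table and implanted device size is tabulated in SAP 5.5, so patient-level data hold both terms. Only the printed compression summary would not be directly comparable.

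**Conclusion.** The footnotes are wrong as written and conflict with protocol 10.2.2. Four Watchman/FLX rows would show about 168% to 660% where the protocol formula gives 8% to 20%, for 21 to 33 mm devices at 80-92% of nominal size. Devices outside that relative range, or FLX devices outside those nominal sizes, would give other figures, but the missing divisor does not depend on them. The row labels are misleading and should be renamed.

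The importance is low. Protocol 10.2 places the adjunctive CCTA analyses outside the study endpoints, and SAP 5.9 says these assessments are not directly comparable between devices. The table has one device column and no p-value. Compression enters none of the primary, secondary, safety or feasibility outcomes, and no analysis population or subgroup. A reader might infer from the size of the percentages that a trial result is at risk; none is.

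**What to change.** In SAP Supplemental Table 2, replace both footnotes with (manufacturer device diameter − measured diameter)/manufacturer device diameter × 100%, using the maximum measured diameter in one and the minimum in the other. Rename the rows *Compression at maximum diameter* and *Compression at minimum diameter* in both the TEE and CCTA blocks. Renaming is enough; the rows need not be swapped.

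The cost is two footnotes and four row labels. No new data are needed, and no other analysis changes.
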